7.2.3. Visit 3 (Week 1 ± 2 days)

- 1. Record any changes to concomitant medications.
- 2. Perform a complete neurological physical exam, including visual field assessment, fundoscopic exam, cranial nerve exam, peripheral motor and sensory fields, and reflexes.
- 3. Perform and record vital signs, including blood pressure monitoring.
- 4. Administer migraine-related symptom scores (i.e., MIDAS, 4-point Verbal Rating Scale, 11-point Numeric Pain Rating Scale).
- 5. Review Subject Diary, including any incidence of adverse events.
- 6. Schedule subject for Visit 4.

7.2.4. Visit 4 (Week 6 ± 2 days)

- 1. Record any changes to concomitant medications.
- 2. Perform a complete neurological physical exam, including visual field assessment, fundoscopic exam, cranial nerve exam, peripheral motor and sensory fields, and reflexes.
- 3. Perform and record vital signs, including blood pressure monitoring.
- 4. Administer migraine-related symptom scores (i.e., MIDAS, 4-point Verbal Rating Scale, 11-point Numeric Pain Rating Scale).
- 5. Review Subject Diary, including any incidence of adverse events.
- 6. Schedule subject for Visit 5.

7.2.5. Visit 5 (Week 12 ± 2 days)

- 1. Record any changes to concomitant medications.
- 2. Perform a complete neurological physical exam, including visual field assessment, fundoscopic exam, cranial nerve exam, peripheral motor and sensory fields, and reflexes.
- 3. Perform and record vital signs, including blood pressure monitoring.
- 4. Administer migraine-related symptom scores (i.e., MIDAS, 4-point Verbal Rating Scale, 11-point Numeric Pain Rating Scale).
- 5. Review Subject Diary, including any incidence of adverse events.

8. DATA SAFETY MONITORING

8.1. Safety Monitoring Plan

Data safety monitoring will be undertaken jointly by the Institutional Review Board and Investigator, including training all co-investigators to report research-related adverse events to Investigator within 12 hours. A safety report to the Institutional Review Board after either

reaching half of anticipated enrollment (10 subjects) or eight months following trial start, whichever event occurs first, will be prepared.

An adverse event (AE) is any untoward medical occurrence in a clinical investigation of a patient administered a pharmaceutical product and that does not necessarily have a causal relationship with the treatment. An AE is therefore any unfavorable and unintended sign (including an abnormal laboratory finding), symptom or disease temporally associated with the administration of an investigational product, whether or not related to that investigational product. An unexpected AE is one of a type not identified in nature, severity, or frequency in the current Prescribing Information or of greater severity or frequency than expected based on the information in the Prescribing Information.

The Investigator will probe, via discussion with the subject, for the occurrence of AEs during each subject visit and record the information in the site's source documents. Adverse events will be recorded in the patient study records. Adverse events will be described by duration (start and stop dates and times), severity, outcome, treatment and relation to study drug, or if unrelated, the cause.

AE Severity

The National Cancer Institute's Common Terminology Criteria for Adverse Events (CTCAE) Version 3.0 will be used to assess and grade AE severity, including laboratory abnormalities judged to be clinically significant. The modified criteria can be found in the study manual. If the experience is not covered in the modified criteria, the guidelines shown in Table 2 below should be used to grade severity.

Severity (Toxicity Grade)	Description
Mild (1)	Transient or mild discomfort; no limitation in activity; no
	medical intervention or therapy required. The subject may be
	aware of the sign or symptom but tolerates it reasonably well.
Moderate (2)	Mild to moderate limitation in activity, no or minimal medical
	intervention/therapy required.
Severe (3)	Marked limitation in activity, medical intervention/therapy
	required, hospitalizations possible.
Life-threatening (4)	The subject is at risk of death due to the adverse experience as it
	occurred. This does not refer to an experience that
	hypothetically might have caused death if it were more severe.

Table 2. AE Severity Grading

AE Relationship to Study Drug

The relationship of an AE to the study drug will be assessed using the following the guidelines in Table 3.

Relationship to Drug	Comment
Definitely	Previously known toxicity of agent; or an event that follows a reasonable temporal sequence from administration of the drug; that follows a known or expected response pattern to the suspected drug; that is confirmed by stopping or reducing the dosage of the drug; and that is not explained by any other reasonable hypothesis.

 Table 3. AE Relationship to Study Drug

Probably	An event that follows a reasonable temporal sequence from administration of
	the drug; that follows a known or expected response pattern to the suspected
	drug; that is confirmed by stopping or reducing the dosage of the drug; and
	that is unlikely to be explained by the known characteristics of the subject's
	clinical state or by other interventions.
Possibly	An event that follows a reasonable temporal sequence from administration of
	the drug; that follows a known or expected response pattern to that suspected
	drug; but that could readily have been produced by a number of other factors.
Unrelated	An event that can be determined with certainty to have no relationship to the
	study drug.

An SAE is defined as any AE occurring at any dose that results in any of the following outcomes:

- death
- a life-threatening adverse experience
- inpatient hospitalization or prolongation of existing hospitalization
- a persistent or significant disability/incapacity
- a congenital anomaly/birth defect

Other important medical events may also be considered an SAE when, based on appropriate medical judgment, they jeopardize the subject or require intervention to prevent one of the outcomes listed.

All personnel will document all SAEs that occur (whether or not related to study drug). The collection period for all SAEs will begin after study drug administration and end after the final study visit have been completed.

Consistent with federal regulations and in accordance with standard operating procedures and policies of the Cooper University Health Care Institutional Review Board (IRB), all potential unanticipated problems that are 1) unforeseen and 2) indicate that participants are at increased risk of harm will be promptly reported to the Cooper University Health Care IRB. The Investigator will report internal and external AEs to the Cooper University Health Care IRB within 7 days of discovery that meet above criteria for an unanticipated problem requiring prompt reporting to the IRB. SAEs meeting prompt reporting criteria will be reported to the Cooper University Health Care IRB within 7 days of notification. Full reports will include: a) whether the occurrence of the adverse event alters the risk-benefit relationship of study participation, b) whether the protocol and/or consent form require modification, and c) whether any additional information needs to be given to the subjects who are already enrolled. Per federal regulations, SAEs meeting prompt reporting criteria will be reported within 7 calendar days if life-threatening or fatal or within 15 calendar days for all other types of qualifying reportable events to the appropriate regulatory body (i.e., FDA).

Monitoring visits will be conducted by representatives of the Sponsor according to the U.S. CFR Title 21 Parts 50, 56, and 312 and ICH Guidelines for GCP (E6). The Investigator grants permission to appropriate regulatory authorities to conduct on-site monitoring and/or auditing of all appropriate study documentation.

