4. STUDY OBJECTIVES

4.1. Primary Objective

Primary outcome is safety of the lidocaine and methylprednisolone co-administration intra-arterially into the middle meningeal arteries. The endpoints that will be analyzed to examine this outcome include: incidence of all adverse events; incidence of adverse events attributed to the study drug; and incidence of any serious adverse events.

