5.3. Number of Subjects to be Evaluated

Up to 10 patients will be evaluated. Sample size was determined off of norms for phase 1 trials, as there lacks sufficient data to conduct a power analysis. Patients who are lost to follow-up and/or withdraw early from the study will not be replaced.

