6. SUBJECT SELECTION

6.1. Inclusion Criteria

1. Male or female ≥ 18 years of age.

- 2. Documentation of a diagnosis of intractable migraine without aura, including failure of at least four classes of preventative drugs. Either intolerance or side effects requiring early discontinuation or adequate trial at therapeutic dose without relief constitutes failure of therapy.
- 3. Written informed consent obtained from subject and ability for subject to comply with the requirements of the study.

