6.4. Screening

Upon enrollment, the neurological provider will be asked to verify past medical history (i.e., tobacco use, obesity status, past traumatic brain injury, diabetes mellitus, hypertension, hyperlipidemia) and current medications during the clinical encounter. Patients would undergo a pre-treatment serum metabolic blood panel to document baseline serum glucose levels, which is a routine biomarker to assess prior to administering glucocorticoid medications. Specific for research purposes only, patients would also be asked to score baseline MIDAS, 4-point verbal rating scale, and 11-point numeric pain scores (Appendix G). Patients will be instructed to keep a Study Diary, and will be instructed to record migraine episodes and any adverse events with date of onset, duration, and description for four weeks before and three months after treatment.

Patients with baseline serum glucose of above 400 mg/dL will fail screening procedures and not be included within the study due to elevated risk of acute exacerbation of steroid hyperglycemia during methylprednisolone administration.

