9. STATISTICAL METHODS AND CONSIDERATIONS

9.1. Analysis Plan

An intention to treat analysis will be performed. Prevalence of any adverse event, treatment-related adverse events, and serious and/or fatal adverse events will be calculated. Secondary analyses assessing pairwise differences in pre- and post-interventional changes in symptom scores will also be performed to identify trends and as the basis for future power analyses. Categorical variable data will be summarized as frequencies with Agresti-Coull intervals as applicable. Quantitative variable data will be summarized as medians with interquartile ranges. Spearman's rank correlation coefficient, two-sided Student's t-test, chi-square tests, and nonparametric equivalences may be conducted at 0.05 significance level.

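### Read literally, the AE definition counts a patient's habitual migraine attacks, so the primary any-AE incidence would mostly measure the disease

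*Combined protocol and SAP*

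**What the plan says.** Section 8.1 (Safety Monitoring Plan) sets the AE definition: "An AE is therefore any unfavorable and unintended sign (including an abnormal laboratory finding), symptom or disease temporally associated with the administration" of the product, "whether or not related to that investigational product". It makes no exception for symptoms of the disease under study. The investigator asks about AEs at every visit, and the last visit is at week 12 (7.2.5).

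Section 4.1 names three primary safety endpoints: "incidence of all adverse events; incidence of adverse events attributed to the study drug; and incidence of any serious adverse events". Section 9.1 carries them into the analysis: "Prevalence of any adverse event, treatment-related adverse events, and serious and/or fatal adverse events will be calculated". It adds: "Categorical variable data will be summarized as frequencies with Agresti-Coull intervals as applicable".

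The population is defined in 6.1 by "Documentation of a diagnosis of intractable migraine without aura, including failure of at least four classes of preventative drugs". No minimum or maximum attack frequency is set. Section 5.3 fixes the size: "Up to 10 patients will be evaluated". Section 5.1 describes one open-label, non-randomized group.

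The diary is described in 6.4: patients "will be instructed to record migraine episodes and any adverse events with date of onset, duration, and description for four weeks before" treatment and for three months afterwards. It therefore names migraine episodes and AEs as two items. No section says how they relate, and no AE or analysis rule uses the pre-dose diary as a reference. The diary-review step mentions migraine episodes at Visit 2 (7.2.2) but only AEs at Visits 3 to 5 (7.2.3 to 7.2.5).

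**The concern.** A migraine attack is an unfavorable symptom. One that occurs after dosing, within the period in which AEs are collected, fits the wording of 8.1 whatever its cause. Patients who have failed at least four preventive classes can be expected to go on having attacks. If the site follows the text, the first-listed primary endpoint fills with the natural course of the disease. An observed 9/10 or 10/10 would then say little about the safety of the injection. With a single arm, there is no comparator from which to estimate the background.

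The diary wording leaves room for another practice: a site may log every headache as a migraine episode and not consider it as an AE. A treatment-induced increase in attacks, or a headache provoked by the procedure, could then be left out of the primary count.

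The trial's main purpose is to characterize safety, so its first-listed endpoint should not depend on how the site resolves this. The same question arises for an admission for migraine, because the SAE definition in 8.1 starts from an AE.

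**Working it through.** The plan states no expected AE or attack rate, so there is no figure of its own to reproduce. The calculations below are for scale.

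**Inputs from the documents:** up to 10 patients (5.3); 12 weeks of post-dose follow-up (7.2.5), or three 4-week windows; a 4-week pre-dose diary (6.4); Agresti-Coull intervals (9.1).

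**Assumptions:** attacks follow a Poisson process at r per 4 weeks, with no treatment effect; the confidence level is 95% (9.1 does not state one).

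**Step 1. AE cases from migraine alone, literal reading.** P(at least one attack in 12 weeks) = 1 − exp(−3r). The chance that all 10 patients are cases is this value to the 10th power.

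| r per 4 weeks | P(≥1 attack) | Expected of 10 | P(all 10) |
|---|---|---|---|
| 0.25 | 53% | 5.3 | 0.2% |
| 0.5 | 78% | 7.8 | 8% |
| 1 | 95% | 9.5 | 60% |
| 2 | 99.8% | 9.98 | 98% |

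**Step 2. What this does to the reported figure.** Let q be the risk of a non-migraine AE, assumed independent of attacks. The pooled any-AE risk is 1 − (1 − q)·exp(−3r).

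- q = 10%: 80% (r = 0.5), 95.5% (r = 1), 99.8% (r = 2).
- q = 30%: 84%, 96.5%, 99.8%.
- q = 50%: 89%, 97.5%, 99.9%.

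At one attack per 4 weeks, moving q from 10% to 50% shifts the pooled figure by only 2 percentage points (95.5% to 97.5%). The endpoint can hardly register a fivefold difference in other AEs.

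Agresti-Coull interval: n' = 10 + 1.96² = 13.84; p' = (x + 1.92)/13.84; limits p' ± 1.96·√(p'(1 − p')/13.84).

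- Migraine kept apart, x = 3: p' = 0.356, interval 10% to 61%.
- Migraine pooled in, x = 10: p' = 0.861, interval 68% to 100% (upper limit 104% before truncation).

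**Step 3. Which rule for worsening would work.** Suppose any rise over the pre-dose diary counted as an AE. With B attacks in the baseline window and no treatment effect, the chance that at least one of three post-dose windows exceeds B is 1 − Σ P(B = b)·F(b)³, where F is the Poisson distribution function. This gives 62%, 66%, 68% and 70% at r = 1, 2, 4 and 8. Six or seven patients of 10 would be flagged by chance, so a margin is needed.

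**The case against.** A reader might infer that the plan forces a choice between an endpoint saturated by disease and one that excludes every headache. The documents do not support the second half. The diary text is a recording instruction to patients. It does not make the two entries mutually exclusive, and it does not override 8.1, under which the investigator identifies AEs. A new headache type or a treatment-induced worsening falls within that definition. A sensible site could treat habitual attacks as disease and worsening as an AE without contradicting either section. This stands: omission of worsening is a possible practice, not the protocol's rule.

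Nor would worsening vanish from the trial. MIDAS, both pain scales, a neurological examination and diary review take place at weeks 1, 6 and 12. At worst, worsening is missed in the AE count.

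It can also be said that saturation affects mainly one of three endpoints, that severity, cause and relationship are recorded for each AE, and that no decision threshold rests on the any-AE proportion. This is largely right. The drug-attributed and SAE endpoints are less exposed, though not immune. The unrelated category in Table 3 demands certainty, there is no unlikely category, and an attack soon after dosing is hard to place. The recorded fields would allow habitual attacks to be separated afterwards, but 9.1 does not plan that.

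The study manual's modified CTCAE criteria are not among the documents. Section 8.1 describes them as a means of grading severity, not of deciding what is an AE.

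Finally, the attack rates are assumptions. At 0.25 per 4 weeks, about half the patients, not nearly all, would be cases from migraine alone.

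**Conclusion.** The point holds in a limited form. Applied as written, 8.1 makes a habitual post-dose attack an AE, and the primary any-AE incidence would be dominated by the disease: 53% to 99.8% of patients from migraine alone across assumed rates of 0.25 to 2 attacks per 4 weeks, and 95% or more from one attack per 4 weeks upward. This rests on the Poisson model, on a rate that the documents do not give, and on no treatment effect on attacks.

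The missing link between the diary's two entries also allows a site to leave worsening out of the AE count. It would be wrong to conclude that the plan requires this, that worsening would go unseen in all data, or that the whole safety result is unreadable. The defect is confined mainly to one primary figure, but that figure is listed first, and it can be made interpretable at little cost.

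**What to change.** In 8.1, state that a post-dose attack consistent with the patient's own four-week pre-dose diary is recorded as a migraine episode. Record as an AE any of the following:

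- a new headache type;
- a new neurological symptom;
- headache starting during the procedure or recovery;
- an increase in attack frequency or duration over the pre-dose diary beyond a margin that the sponsor fixes in advance. Any increase at all should not be the trigger, for the reason in Step 3 of the working.

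State that any attack with an SAE outcome is recorded as an SAE.

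In 9.1, report any-AE incidence twice: with and without headache and migraine events.

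The cost is a few sentences, one extra table row, and a comparison with the diary for borderline attacks. The diary already collects the reference data. The sponsor must choose and justify the margin, and a four-week baseline is short, so some chance flags will remain.

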No specific methylprednisolone-related risks are anticipated for the investigational dosing amount and route. The following are potential complications for methylprednisolone use per Section 5 (WARNINGS AND PRECAUTIONS) for the Prescription Drug Labeling of NDA 011856. Complications with methylprednisolone treatment are dependent on dosage size, duration, and route of administration. Methylprednisolone has been associated with rare serious neurological adverse events, including spinal cord infarction, paraplegia, quadriplegia, cortical blindness, and stroke, with epidural administration. There have been rare reports of anaphylactoid reactions. Large doses of corticosteroids have been associated with elevated blood pressure and increased potassium and calcium excretion. After recent myocardial infarction, there has been a suggested association between drugs within the corticosteroid pharmacologic class and left ventricular free wall rupture. Chronic methylprednisolone use is associated with hypothalamic-pituitary adrenal axis suppression, Cushing's syndrome, and hypoglycemia. High doses of cyclic, pulsed methylprednisolone administration are associated with toxic acute hepatitis. Corticosteroid use is associated with increased susceptibility to infections, including fungal infections.

Other risks of participation include very rare adverse events related to route of administration, including allergic response to agents, vessel injury, access site hematoma, and infection.

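### Table 3 lets a known toxicity be graded Definitely related with no timing or alternative-cause test, which can overstate the primary drug-attributed adverse event incidence

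*Combined protocol and SAP*

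**What the plan says.** Section 4.1 makes "incidence of adverse events attributed to the study drug" one of three primary safety endpoints, beside the incidence of all adverse events (AEs) and of serious AEs. Section 9.1 plans to report the prevalence of treatment-related AEs, with Agresti-Coull intervals for categorical data. Neither section says which causality grades make an event attributed or treatment-related.

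The grading comes from Section 8.1: "The relationship of an AE to the study drug will be assessed using the following the guidelines in Table 3". The table has four grades.

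- **Definitely** begins "Previously known toxicity of agent; or an event that follows a reasonable temporal sequence from administration of the drug". The part after 'or' goes on to require a known or expected response pattern, confirmation when dosing is stopped or lowered, "and that is not explained by any other reasonable hypothesis".
- **Probably** requires timing, pattern and the same confirmation, and that the subject's clinical state or other interventions are unlikely explanations.
- **Possibly** requires timing and pattern, "but that could readily have been produced by a number of other factors".
- **Unrelated** is "An event that can be determined with certainty to have no relationship to the" study drug.

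Among potential methylprednisolone complications, Section 3.4.1 states: "Corticosteroid use is associated with increased susceptibility to infections, including fungal infections". It also states: "Large doses of corticosteroids have been associated with elevated blood pressure". The same section expects no specific methylprednisolone risk at the trial's dose and route.

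Treatment is given once (Section 2). AEs are sought at each visit, the last at Week 12 (Sections 7.2 and 8.1). Up to 10 patients are evaluated (Section 5.3).

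**The concern.** A causality scale should ask for more evidence as the grade rises. Here the top grade has an entry route that asks for less than the two grades below it. An event qualifies through that route because of what kind of event it is, whatever its timing and whatever else could explain it.

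Table 3 is the only stated basis for attributing an event to the drug, and attribution defines a primary endpoint. A coincidental event of a recognised type could therefore enter the drug-attributed count, or be recorded there with more certainty than the evidence supports. Section 3.1 intends the safety results as the basis for larger studies, so the error would be carried forward.

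**Working it through.** The plan gives no expected AE rate and no power calculation, so there is no figure to reproduce. The main check is textual; the arithmetic only shows scale.

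**Step 1: conditions for each grade.**

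| Route | Timing | Known pattern | Confirmed on stopping or reducing | Other causes |
|---|---|---|---|---|
| Definitely, before 'or' | no | known toxicity | no | no condition |
| Definitely, after 'or' | yes | yes | yes | excluded |
| Probably | yes | yes | yes | unlikely |
| Possibly | yes | yes | no | may be present |
| Unrelated | – | – | – | certainty of no relationship |

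The clauses that follow 'or' describe the event named after it, so on the plain reading they do not reach back to the known-toxicity route. Because treatment is given once, confirmation by stopping or reducing cannot be observed after the session. For later events the unconditioned route is then the only practical way to reach Definitely.

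**Step 2: does the endpoint change?** Take a coincidental event of a known type. The literal first route grades it Definitely. Without that route:

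- If its timing is plausible and it fits a known pattern, it is Possibly.
- If its timing is not plausible, it fails Definitely, Probably and Possibly, and it is Unrelated only if that is certain. Otherwise it has no grade.

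| Grades counted as attributed | Plausible timing | No plausible timing |
|---|---|---|
| Definitely only | added to the count | added to the count |
| Definitely and Probably | added to the count | added to the count |
| Definitely, Probably and Possibly | counted either way; only the grade rises | added to the count |

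**Step 3: scale.** One patient of 10 is 1/10 = 10 percentage points, provided that patient has no other attributed event. The 95% Agresti-Coull intervals, cut off at zero, are:

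| Count | Rate | Interval |
|---|---|---|
| 0/10 | 0% | 0 to 32.1% |
| 1/10 | 10% | 0 to 42.6% |
| 2/10 | 20% | 4.6 to 52.1% |
| 3/10 | 30% | 10.3 to 60.8% |

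**Step 4: upper bound for infections.** Assumptions, not in the documents: infections follow a Poisson distribution with mean r per patient over 12 weeks, there is no drug effect, and every infection is graded Definitely. Then P(at least one) = 1 − exp(−r).

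| r | P(at least one) | Expected patients of 10 |
|---|---|---|
| 0.1 | 9.5% | 1.0 |
| 0.2 | 18.1% | 1.8 |
| 0.3 | 25.9% | 2.6 |
| 0.5 | 39.3% | 3.9 |

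If only half of the infections were graded Definitely (again an assumption), the means halve. At r = 0.1 the result is 1 − exp(−0.05) = 4.9%, or 0.5 of 10. At r = 0.5 it is 1 − exp(−0.25) = 22.1%, or 2.2 of 10.

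**The case against.** **Inflation is not shown.** This stands in part. Which grades count is unstated, and if Possibly counts, many such events are in the numerator anyway. What remains is the added count from events without plausible timing, and the promotion of the others to Definitely, which would mislead any breakdown by grade.

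**The examples stretch the text.** A reader might infer that ordinary blood pressure rises weeks later would be graded Definitely. The documents do not support that: Section 3.4.1 ties blood pressure to large doses and says that complications depend on dose size, duration and route. The infection example is stronger because its sentence carries no dose limit. Even so, it speaks of susceptibility, and an investigator could decline to call a late cold a toxicity of the drug.

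**Other wording supplies safeguards.** Section 8.1 defines an AE as temporally associated with administration, asks for a cause when an event is judged unrelated, and calls Table 3 guidelines. These help little. The AE definition has no time window and covers unrelated events too, so it cannot separate related from unrelated. A cause is asked for only after an event has been judged unrelated. No other relatedness rule is given.

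**The later conditions might govern both routes.** This reading is less natural. Even on it, 'or' leaves known toxicity as an alternative to the timing clause.

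**The consequence is limited.** This stands. The analysis is descriptive, no stated decision rule uses the attributed count, and the incidence of all AEs is reported beside it.

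**Rewording the first route alone is not enough.** This stands too. A late infection without plausible timing would then usually have no grade, because Unrelated demands certainty.

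**Conclusion.** The defect is in the stated rule. On its plain reading, Table 3 gives its highest grade to a known toxicity without the timing test that the next two grades require and without any test of other causes. This can inflate the drug-attributed incidence or overstate the certainty behind it, at 10 percentage points for each patient added out of 10.

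The total size is not determined. A reader might infer that one to four patients will be wrongly counted. The documents do not support that: 1.0 to 3.9 of 10 rests on assumed infection rates of 0.1 to 0.5 per 12 weeks and on every infection being graded Definitely. The added count falls if fewer are so graded, and it is zero for events that would have counted as Possibly anyway. Nor do the documents show that the endpoint would merely measure everyday illness, since investigators still judge what is a toxicity of the drug.

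The correction should be made before any AE is graded, because the rule feeds a primary endpoint and is cheap to repair.

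**What to change.** Make three linked wording changes.

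1. In the Definitely row of Table 3, replace the opening route with: *a previously known toxicity of the agent that follows administration in a reasonable temporal sequence* "and that is not explained by any other reasonable hypothesis". Known toxicity then supports the grade without deciding it alone.
2. So that events failing this test have a grade, either remove the certainty requirement from Unrelated or add an Unlikely grade between Possibly and Unrelated.
3. In Section 9.1, state which grades count as treatment-related, and use the same definition for the attributed-AE endpoint in Section 4.1.

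The reworded route still omits the confirmation-on-stopping condition that Probably keeps, so the order of the grades is not fully repaired on that one criterion. As shown above, that criterion cannot be observed after the single session, so the sponsor should check whether it belongs in the scale.

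The cost is one sentence for the first change and short text edits for the other two. No added data, visits or patients are needed.
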